8.3.3. Treatment Comparisons

Demographic and baseline characteristics (e.g., gender, age, racial or ethnic origin, height and weight, body mass index (BMI), blood pressure and other characteristics) will be summarized for each treatment group. In addition, smoking and alcohol habits, diabetic and cardiovascular medical history, baseline laboratory results, and prior medications will be summarized by treatment group. Binary and ordinal characteristics will be summarized by counts and percentages, while continuous variables will be represented by mean and standard deviations or medians and percentiles, as appropriate. Any variables with treatment imbalances may be considered as covariates for further analysis of an exploratory nature. Such covariates will be identified on the basis of the clinical relevance of the observed treatment difference.

8.3.3.1. Primary Comparisons of Interest

The primary endpoint will be the time to the first occurrence of MACE over the full duration of the study. A p-value for the primary endpoint will be calculated from a Cox regression model with treatment group as the only covariate for the hypotheses described in Section 8.1.

8.3.3.2. Other Comparisons of Interest

For other analyses incidence rates will be presented for binary data and summary statistics (mean, median, standard deviation, minimum, and maximum) will be presented for continuous data. Furthermore, summary statistics of change from baseline for HbA1c will be presented along with percent of subjects within ranges of clinical interest (e.g., HbA1c < 7.0%).

[figure not shown]
8.3.4. Interim Analysis

An IDMC will monitor progress of the study and ensure that it meets the highest standards of ethics and subject safety. All cardiovascular event data, together with other safety data, will be sent to the IDMC for review at approximately every 6 months after the first subject has been randomised to receive treatment. This frequency may be adjusted, if deemed necessary by the IDMC, depending on the enrolment rates and the rate of safety events. There are no plans to stop the study early for a non-inferiority or benefit claim, however should the IDMC identify in the course of its scheduled reviews overwhelming evidence of MACE benefit (e.g., $p < 0.001$), with directionally consistent findings on all-cause mortality, the IDMC might consider recommending early stopping. This approach essentially preserves the final alpha for the end-of-study analysis at 5% and hence there are no plans to adjust the final alpha on account on safety reviews conducted by the IDMC. The IDMC charter, reporting and procedures are outlined in separate documents.

8.3.5. Multiplicity Controls

A multiple comparisons adjustment strategy will be implemented for the multiple inferential tests among the primary endpoint and secondary endpoints of MACE superiority, time to insulin and composite metabolic endpoint.

The strategy will use a combination of gatekeeper and Hommel procedure. The first step is to evaluate the MACE non-inferiority of the albiglutide group vs the placebo group at a one-sided $\alpha=0.025$ level. If the result of non-inferiority is significant, MACE superiority, time-to-insulin and composite metabolic endpoint will be tested simultaneously using the Hommel procedure with $\alpha=0.05$. The above multiplicity control approach will preserve the study's nominal significance level of 0.05. The test order is illustrated in the diagram below.

Hommel Procedure for secondary endpoints is described below:

Three hypothesis tests for MACE superiority, time-to-insulin, and composite metabolic endpoint are subject to be adjusted by the Hommel procedure. Let $P(1)$, $P(2)$ and $P(3)$ represent the ordered p-values that $P(3) > P(2) > P(1)$ and $H(1)$, $H(2)$ and $H(3)$ are corresponding hypotheses.

If $P(3) < 0.05$, reject $H(3)$, $H(2)$, $H(1)$. End of test.

If $P(3) \geq 0.05$ and $P(2) < 0.05/2$, accept $H(3)$, reject $H(2)$, $H(1)$. End of test.

If $P(3) \geq 0.05$ and $P(2) \geq 0.05/2$ and $P(1) < 0.05/3$, accept $H(3)$, $H(2)$, reject $H(1)$. End of test.

If $P(3) \geq 0.05$, $P(1) \geq 0.05/3$ and $0.05/2 \leq P(2) < 0.05 \cdot 2/3$, accept $H(3)$, $H(2)$, reject $H(1)$. End of test.

If $P(3) \geq 0.05$, $P(2) \geq 0.05 \cdot 2/3$ and $P(1) \geq 0.05/3$, accept $H(3)$, $H(2)$ and $H(1)$.

Other Secondary Endpoints and Subgroup Analysis

The following secondary endpoints will provide supportive evidence for cardiovascular safety and will not use any multiplicity adjustment procedure.

- Components of primary endpoint (MACE = cardiovascular death, MI, stroke)
- MACE + urgent revascularisation for unstable angina
- Cardiovascular death or hospitalisation for heart failure

Other secondary endpoints which do not qualify for formal statistical hypothesis testing will be analyzed and have results presented with confidence interval and nominal p-values:

- Mean HbA1c at scheduled visits and change from baseline
- Mean body weight at scheduled visits and change from baseline
- Mean eGFR at scheduled visits and change from baseline
- Time to initiation of prandial insulin
- Composite microvascular endpoint

To examine the degree of consistency of the overall treatment effect in terms of important prognostic factors, subgroup analyses of the primary outcomes will be performed based on subject demographics and baseline characteristics. These exploratory subgroup analyses will not be adjusted for multiple comparisons and will be interpreted descriptively.

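### Line 4 of the written Hommel rule in Section 8.3.5 omits P(1) < 0.025, so it can declare a secondary claim at p up to 0.033 where Hommel declares none

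*Protocol*

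**What the plan says.** Section 8.3.5 of the protocol sets up a gatekeeper followed by a family of three. The gate is MACE non-inferiority: "The first step is to evaluate the MACE non-inferiority of the albiglutide group vs the placebo group at a one-sided $\alpha=0.025$ level". If it passes, the three secondary hypotheses "will be tested simultaneously using the Hommel procedure with $\alpha=0.05". The section repeats the method by name, "Three hypothesis tests for MACE superiority, time-to-insulin, and composite metabolic endpoint are subject to be adjusted by the Hommel procedure", and orders the p-values so that P(1) is the smallest and P(3) the largest.

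It then writes the procedure out as five decision lines. In shorthand:

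1. P(3) < 0.05: reject all three.
2. P(3) ≥ 0.05 and P(2) < 0.025: reject H(2) and H(1).
3. P(3) ≥ 0.05, P(2) ≥ 0.025 and P(1) < 0.0167: reject H(1) only.
4. "If $P(3) \geq 0.05$, $P(1) \geq 0.05/3$ and $0.05/2 \leq P(2) < 0.05 \cdot 2/3$, accept $H(3)$, $H(2)$, reject $H(1)".
5. P(3) ≥ 0.05, P(2) ≥ 0.0333 and P(1) ≥ 0.0167: reject none.

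On error control it states: "The above multiplicity control approach will preserve" the nominal 0.05 level.

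Section 8.3.5 appears twice in the protocol file, in the Amendment 1 text and in the protocol that preceded it, and the five lines are the same in both. The list of specific changes for Amendment 2 (Appendix 9, Section 11.9.2) edits Sections 8.3.3.1, 8.3.3.2, 8.3.6.2, 8.3.6.4 and 8.3.6.5, but not 8.3.5.

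**The concern.** Line 4 gives P(1) a lower bound (0.05/3) and no upper bound. The only ceiling is the ordering P(1) < P(2), and P(2) may be anything below 0.0333. The line therefore rejects H(1) with P(1) anywhere from 0.0167 to just under 0.0333. The Hommel procedure stops at 0.025 in this region.

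This rule governs the only alpha-controlled secondary claims in the trial, one of which is cardiovascular superiority. If the results fell in the affected region, standard Hommel software and the written lines would give opposite answers. The sponsor would then have to choose between them after seeing the data. The discrepancy runs one way only: the written rule adds rejections and never removes one.

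**Working it through.** **Inputs (all from Section 8.3.5).** Three hypotheses, α = 0.05, P(1) < P(2) < P(3), and the five lines above.

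**What Hommel requires where line 4 applies.** Hommel is the closed test built on Simes tests. H(1) is rejected only if every intersection containing it is rejected by Simes. Take P(3) > 0.05 and 0.025 ≤ P(2) < 0.0333:

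| Intersection | Simes rejects if | Met? |
|---|---|---|
| {1,2,3} | P(1) ≤ 0.0167 or P(2) ≤ 0.0333 or P(3) ≤ 0.05 | yes, through P(2) |
| {1,2} | P(1) ≤ 0.025 or P(2) ≤ 0.05 | yes, through P(2) |
| {1,3} | P(1) ≤ 0.025 or P(3) ≤ 0.05 | only if P(1) ≤ 0.025 |
| {1} | P(1) ≤ 0.05 | yes |

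The pair {1,3} supplies the missing condition. In Hommel's index form, j = 3 fails because P(2) < 2α/3 and j = 2 holds, so the critical value is α/2 = 0.025.

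**Example.** p-values 0.030, 0.032 and 0.40.
- Written rule: line 4 applies and H(1) is rejected.
- Hommel-adjusted p for H(1) is the largest Simes p over its intersections. {1,2,3}: min(3 × 0.030, 1.5 × 0.032, 0.40) = 0.048. {1,2}: min(0.060, 0.032) = 0.032. {1,3}: min(0.060, 0.40) = 0.060. {1}: 0.030. The maximum is 0.060.
- The other adjusted values are 0.064 and 0.40. Nothing is significant.

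By contrast, 0.020, 0.030 and 0.40 gives an adjusted p of 0.045 for H(1), and both rules reject it.

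**Exhaustive comparison.** The five lines were coded literally and compared with the Hommel procedure on 4,000 p-value triples drawn from 0 to 0.08. That range was chosen to exercise the rule, so the counts are not frequencies to expect in a trial. All disagreements lay in 0.025 < P(1) < P(2) < 0.0333 with P(3) ≥ 0.05. With P(1) < 0.05/2 added to line 4 there were none. Lines 1, 2, 3 and 5 are correct.

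**Size on average.** With three independent true nulls the discordant region has probability 3 × (0.0333 − 0.025)² × 0.95 ≈ 0.0002. Simulated familywise error (8 million draws per scenario, independent two-sided tests):

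| Scenario | Written rule | Hommel |
|---|---|---|
| Global null | 0.0499 | 0.0497 |
| One real effect, z-shift 2.19 | 0.0425 | 0.0421 |
| One real effect, z-shift 4 | 0.0495 | 0.0494 |

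**Size at the extreme.** Hold one p-value at c, with 0.025 < c < 0.0333, and let the other two hypotheses be true nulls. The written rule makes a false claim if both null p-values are below 0.05 (line 1, probability 0.05² = 0.0025), or if one is below c while the other is at least 0.05 (probability 2 × c × 0.95). The total is 2 × c × 0.95 + 0.0025:
- c = 0.026: 0.0494 + 0.0025 = 0.052
- c = 0.030: 0.0570 + 0.0025 = 0.060
- c just below 0.0333: 0.0633 + 0.0025 = 0.066

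For Hommel, 0.025 replaces c: 2 × 0.025 × 0.95 + 0.0025 = 0.050.

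**The case against.** The strongest reply is that no real inflation has been shown. The written rule rejects at least one hypothesis exactly when the global Simes test does, so under the global null with independent tests its error is 0.05. With one or two real effects, independent or positively correlated, simulated familywise error stayed at or below 0.05, and the excess over Hommel was about 0.0004 at most. The 6.6% is conditional on one p-value sitting just below 0.0333; it is not an error rate of the trial. All of this stands, and the point should not be presented as material alpha inflation.

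A second reply is that the section names Hommel repeatedly, so an analyst using standard software would get the right answer and the five lines are only its description. That reduces the practical risk but does not remove the contradiction. The lines are explicit decision rules, and nothing in the section says the named method overrides them.

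A third is that the main text of Amendment 2 and the analysis plan are not available here, and Section 8.3.6 lets the analysis plan record deviations. A correction there is possible. The Amendment 2 change list shows none, however, and the protocol itself chose to state the full rule.

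The scope is also narrow. The primary non-inferiority test is untouched. The line matters only if non-inferiority passes, two secondary p-values fall in a window 0.0083 wide, and the third is at least 0.05.

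**Conclusion.** The concern holds. Line 4 of the decision rule in Section 8.3.5 is wrong as written. It lacks the condition P(1) < 0.025 and so raises the critical value for the smallest p-value from 0.025 to 0.0333 in one region. There the protocol contains two incompatible rules for its alpha-controlled secondary claims, including MACE superiority. The assurance that 0.05 is preserved no longer follows from closed testing.

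The average cost in familywise error is negligible: about 0.0002 under the global null and no more than about 0.0004 in the scenarios tried, with the total at or below 0.05. Those figures assume normally distributed test statistics, independent or positively correlated. The contradiction itself needs no assumption beyond the text. It still warrants correction before unblinding, because afterwards any choice between the two readings would be made with the result known.

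**What to change.** Either of two changes is enough.

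- **Repair the lines.** Line 4: if P(3) ≥ 0.05, 0.05/3 ≤ P(1) < 0.05/2 and 0.05/2 ≤ P(2) < 0.05 × 2/3, reject H(1) only. Extend line 5 so that none is rejected also when P(3) ≥ 0.05, P(1) ≥ 0.05/2 and 0.05/2 ≤ P(2) < 0.05 × 2/3. Without that extension those outcomes would fall under no line.
- **Replace the lines.** State that each of the three hypotheses is rejected if its Hommel-adjusted p-value is at most 0.05. This is shorter and matches software output.

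The analysis plan should carry the same wording. The cost is a line or two of text, with no change to sample size, data collection or the primary analysis. A narrow band of favourable results stops counting as significant, as the named procedure already requires.

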8.3.6. Key Elements of Analysis Plan

Any deviations from the original analysis planned in the protocol agreed upon prior to finalization of the RAP, will be described in that document. Any additional changes to the planned analysis in the RAP will be described in the final clinical study report.

8.3.6.1. Primary Analysis

The primary analysis is an ITT analysis of the time to the first occurrence of MACE over the full duration of the study. Time to event analyses will be performed using Cox's Proportional Hazard regression with SAS PHREG with treatment group as the only covariate. Data for subjects without a primary event will be censored.

Treatment differences will be estimated via the hazard ratio and its 95% confidence interval (CI).

The hypothesis of non-inferiority of albiglutide relative to placebo group with hazard ratio less than 1.3 with respect to cardiovascular risk will be tested at the end of the study when ~611 first MACE events are cumulated.

The strength of evidence for non-inferiority will be determined by testing the hypothesis that the observed hazard ratio is significantly different from the null margin of 1.3 (one-sided $p < 0.025$ for such a test being equivalent to the upper 95% confidence limit after multiplicity adjustment for the hazard ratio being less than 1.3). The absolute risk difference per 100 PY and superiority p-value for albiglutide vs. placebo will also be presented.

The product-limit estimates of the probabilities (and their standard errors) of first MACE over time will be computed and displayed as Kaplan-Meier (KM) survival curves for albiglutide and placebo groups. The KM curves will also be presented corresponding to the above comparisons.

The total number of all MACE or any of its components will be analyzed by Poisson regression model. The incidence rate per 100 person-years, relative risk and their 95% CI will be presented. Number of subjects who experienced at least one event, 2 or 3 or more MACE or its components will also be summarized by treatment group.

As sensitivity analyses, the analyses described above will be repeated using events occur while on-treatment and events occur during the period of on-treatment plus 56 days post last dose.

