8.2. Study Design Considerations

8.2.1. Sample Size Assumptions

The primary outcome will be analyzed such that the overall Type 1 error is no greater than 5% (two-sided). Specifically, the non-inferiority assessment of albiglutide compared to placebo will be conducted at 0.05 level, requiring one-sided significance at 0.025.

The power for MACE non-inferiority is calculated via the asymptotic variance and normality of the maximum likelihood estimator for the log-hazard ratio. Assuming a true hazard ratio of 1.0, 611 events will be needed to have 90% power to rule out non-inferiority margin of 1.3 for the hazard ratio with type I error of 0.05. The study duration will be event-driven. A total of 9400 subjects will be enrolled and followed until it is projected that approximately 611 adjudicated MACE events will have occurred. If the observed rate for MACE is 2.0% or 3.0%, the mean follow-up will be 3.2 or 2.2 years respectively, assuming that the number of subjects lost to follow-up accounts for 1% or less.

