- Additional analysis will be performed to assess the incidence rate of recurrent severe hypoglycaemic events between treatment groups during the course of the study. A repeated Poisson regression model including treatment and visit as factors will be used to test treatment difference with offset for person years. An unstructured working correlation matrix will be used in the iterative estimation process. The model-adjusted least square incidence rate for each treatment as well as the treatment difference of the incidence rate will be reported. Events of severe hypoglycaemia will also be summarized descriptively by treatment group. Additional summary by baseline HbA1c, renal status and age subgroup will also be provided.

Further analysis details will be provided in the RAP.

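### Total MACE, which can recur within a subject, is assigned a Poisson regression with no stated allowance for overdispersion or within-subject dependence, so the model-based 95% CI will be somewhat too narrow

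*Protocol*

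**What the plan says.** Section 8.3.6.1 (Primary Analysis), after the Cox model and the Kaplan-Meier displays, adds an analysis of all events: "The total number of all MACE or any of its components will be analyzed by Poisson regression model". The output is an estimate with an interval: "The incidence rate per 100 person-years, relative risk and their 95% CI will be presented". The next sentence plans a tabulation: "Number of subjects who experienced at least one event, 2 or 3 or more MACE or its components". The plan therefore expects more than one event in some subjects. The section then extends its analyses to two further data sets, on treatment and on treatment plus 56 days: "As sensitivity analyses, the analyses described above will be repeated using events occur while on-treatment".

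Section 8.3.6.2 treats the other recurrent endpoint, severe hypoglycaemia, differently: "A repeated Poisson regression model including treatment and visit as factors will be used to test treatment difference with offset for person years", followed by "An unstructured working correlation matrix will be used in the iterative estimation process".

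The change log for Amendment 2 lists edits to several parts of section 8 but none to 8.3.6.1, so the total-MACE wording appears to stand.

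**The concern.** Ordinary Poisson regression sets the variance of a count equal to its mean. For repeat cardiovascular events that is unlikely to hold: subjects differ in underlying risk, and a first event may raise the risk of the next. Either feature makes the variance exceed the mean, and the model-based standard error of the log rate ratio is then too small.

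The authors allowed for within-subject correlation in the hypoglycaemia model but wrote no such allowance for total MACE. A programmer reading the two sections together could reasonably fit an ordinary Poisson model to MACE. Its relative risk and CI would be printed beside the primary hazard ratio and again for the two on-treatment data sets. An interval that is too short could suggest a benefit or harm that the data do not support.

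**Working it through.** **The plan's own figure.** Section 8.2.1 says "Assuming a true hazard ratio of 1.0, 611 events will be needed to have 90% power to rule out non-inferiority margin of 1.3", "requiring one-sided significance at 0.025". Schoenfeld's formula with 1:1 allocation gives 4 × (1.960 + 1.282)² / (ln 1.3)² = 42.03 / 0.06883 = 610.6, so 611 events. The figure reproduces. It concerns time to first MACE under Cox regression and does not depend on the Poisson model.

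**Inputs from the protocol.** N = 9400 subjects; m = 611 subjects with at least one event; MACE rate 2.0% a year with mean follow-up 3.2 years, or 3.0% with 2.2 years (section 8.2.1).

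**Assumption.** The share p of the 611 who have a second event is not in the documents. I take 10% to 30%, with no third events and equal follow-up.

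**Formulae.** With Y the count per subject:
- E(Y) = m(1 + p)/N
- E(Y²) = m(1 + 3p)/N
- φ = Var(Y)/E(Y) = (1 + 3p)/(1 + p) − m(1 + p)/N
- true SE / Poisson SE = √φ
- coverage of the nominal 95% CI = 2Φ(1.96/√φ) − 1

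| p | φ | √φ | coverage |
|---|---|---|---|
| 10% | 1.182 − 0.072 = 1.11 | 1.05 | 93.7% |
| 20% | 1.333 − 0.078 = 1.26 | 1.12 | 92.0% |
| 30% | 1.462 − 0.084 = 1.38 | 1.17 | 90.5% |

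**Benchmark.** With a common rate and full independence, simulated trials gave on average 583 subjects with an event and 602 events at 2.0% a year: 19/583 = 3.3% repeats. Putting p = 0.033 in the formula gives 1.099/1.033 − 0.067 = 1.00, as it should. Shares of 10% to 30% therefore represent real dependence.

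**Cross-check by gamma frailty.** With frailty variance v and mean count 0.02 × 3.2 = 0.064, inflation is 1 + 0.064v. For v = 0.5, 1 and 2 the SE ratio is 1.02, 1.03 and 1.06, and coverage is 94.6%, 94.3% and 93.5%.

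**Cross-check by simulation** (2 × 4700 subjects, 400 trials per scenario, 30% of events fatal, 2.0% a year, third and later events allowed; figures at 3.0% are nearly the same):

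| rate after first event | frailty variance | SE ratio | implied coverage |
|---|---|---|---|
| ×1 | 1 | 1.02 | 94.5% |
| ×3 | 0 | 1.04 | 94.0% |
| ×5 | 0 | 1.08 | 93.1% |
| ×3 | 1 | 1.10 | 92.6% |
| ×5 | 2 | 1.24 | 88.7% |

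With a subject-clustered (sandwich) standard error, simulated coverage averaged about 95% over the 20 scenarios run. Single scenarios ranged from 92.3% to 97.5%, with a Monte Carlo error of about 1.1 points each.

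**The case against.** The strongest reply is that the protocol names only a model family. It does not say that the variance is model-based or that repeat events are taken as independent. Variance estimator, dispersion scale and offset are details that a protocol may leave to the analysis plan, which is not shown here, and section 8.3.6 allows that plan to record departures. This stands in part: the unseen plan may already contain a robust variance. What remains is that the protocol fixes a model and a CI for a count it expects to recur, and allows for dependence in the parallel hypoglycaemia analysis but not here.

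Several stronger readings are tempting and are not supported:

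- *A reader might infer coverage of 88% or less as the expected case.* That needs a material share of third events or strong dependence. For example, if 30% have a second event and 30% of those a third, φ = 1.60 and coverage is 87.9%. Nothing in the documents points to such a pattern.
- *A reader might speak of an inflated type I error.* The protocol plans an estimate and a CI for total MACE, with no test, and the analysis is outside the alpha-controlled family of section 8.3.5.
- *A reader might assume that a myocardial infarction followed by cardiovascular death counts twice.* The text shown gives no rule for counting linked events.
- *A reader might think the unstructured working correlation invalidates the hypoglycaemia analysis.* With the usual GEE robust standard errors, a poor working correlation costs efficiency, not validity. Convergence is a fair practical worry. Four-monthly contacts over the mean follow-up of 2.2 to 3.2 years give about 6 to 9 visits, hence 15 to 36 correlations, and more for subjects followed longer. Failure of that fit was not simulated, and it is a separate matter.

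**Conclusion.** The point holds, at modest size. Followed as written, the total-MACE interval is too narrow under any positive within-subject dependence. If 10% to 30% of the 611 subjects have exactly two events, the standard error should be about 5% to 17% larger, and the nominal 95% CI covers about 93.7% to 90.5%. Under mild dependence the shortfall is a point or less. Third events would push coverage lower; full independence with a common rate would remove the problem. The recurrence share, frailty variance, post-event risk and fatal share are all assumptions.

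The consequence is confined to a supportive estimate and its two on-treatment repeats. The primary conclusion, the sample size and the multiplicity scheme do not change.

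**What to change.** In section 8.3.6.1, or in the analysis plan, specify for total MACE and its components: *Poisson regression with log follow-up offset and robust (sandwich) variance clustered on subject*. Negative binomial regression with the same offset is an acceptable alternative. Apply the same choice to the on-treatment and on-treatment plus 56 days repeats.

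The cost is one sentence and one option in the code, with no new data and no design change. The downside is a slightly wider interval.

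Optional and separate: for severe hypoglycaemia, name an independence or exchangeable working correlation with robust standard errors, at least as the fallback if the unstructured fit does not converge.
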